7.4.2.2 SENSITIVITY ANALYSIS

If the Z-statistic from the primary analysis is less than or equal to the futility boundary, a sensitivity analysis will be conducted that excludes from the ITT population the 14 participants who could have potentially been affected by unblinding. This analysis would use a logistic mixed model with treatment arm, MN risk, and treatment center-group included as covariates. The standardized log odds ratio estimate for treatment arm would be used as the test statistic and compared to the futility boundary in **Table 17**.

7.4.2.3 DECISION CRITERION

If both the primary and sensitivity analysis results meet their corresponding futility boundaries, the trial will be stopped. Otherwise, if one or both of the analyses do not meet their futility boundaries, the trial will continue.

7.4.3 FINAL ANALYSIS

7.4.3.1 PIVOTAL ANALYSIS

The final analysis will be performed after 136 patients become evaluable for Day 28 response. The primary analysis approach will use the ITT population. A logistic mixed model will be used to evaluate the effect of study treatment on Day 28 overall response while accounting for treatment center-group and MN risk category (high vs. standard), with center-group included as a random effect and treatment arm and MN risk as fixed effects. The standardized log odds ratio estimate for treatment arm from this model will be used as the test statistic (Z-statistic) and will be compared to the efficacy boundary in **Table 15**. The proportion of patients with ORR at Day 28 will be described by treatment arm using sample proportions and 95% Wilson score CIs. Adjusted odds ratio estimates from the logistic mixed model of Day 28 overall response will be summarized in a regression table.

7.4.3.2 SENSITIVITY ANALYSIS REGARDING POTENTIAL UNBLINDING INCIDENT (SA1)

A sensitivity analysis will also be conducted that excludes from the ITT population the 14 participants who could have potentially been affected by unblinding. This analysis will use a logistic mixed model with treatment arm, MN risk, and treatment center-group included as covariates. The standardized log odds ratio estimate for treatment arm would be used as the test statistic and compared to the efficacy boundary in **Table 17**. The proportion of patients with ORR at Day 28 will be described by treatment arm using sample proportions and 95% Wilson score CIs. Adjusted odds ratio estimates from the logistic mixed model of Day 28 overall response will be summarized in a regression table.

7.4.3.3 SENSITIVITY ANALYSIS REGARDING JANUARY 2021 STUDY DRUG SUPPLY DISRUPTION (SA2)

Due to a quality control error during the manufacturing process of the study drug, the study drug was recalled, and enrollment was put on hold in January 2021. This hold was lifted in May 2021 with release of version 3.0 of the protocol.

The course of treatment was disrupted for two patients who were still receiving study drug at the time of the drug recall. To evaluate the sensitivity of analysis results to this disruption, we will conduct a sensitivity analysis of the primary endpoint according to the same procedure in Section 7.4.3.1 where any patients whose treatment courses were disrupted by the drug recall are excluded from the ITT analysis population. This analysis would be conducted using the ITT population and a similar estimand as in **Table 16**, with the only modification being the exclusion of the 2 patients affected by the supply disruption from the ITT population.

7.4.3.4 SUPPLEMENTARY ANALYSES

Two supplementary analyses will investigate the potential influence of other variables on the primary analysis' outcome in the ITT population. Two logistic mixed models will be fitted with Day 28 overall response as the outcome. One model will have fixed effects of treatment arm, MN risk, age (under 18 years vs. 18 years or older), and disease type (malignant vs. non-malignant) and a random effect of center-group; the second will also include these covariates in addition to the MAGIC biomarker risk score (1 vs. 2 vs. 3). If no patients under 18 years old are enrolled and randomized, the fixed effect for age will be omitted from the model. The results from the second model may be presented in a separate report depending on the biomarker data availability.

In addition to these protocol-specified supplementary analyses, an additional supplementary analysis will assess Day 28 overall response in comparison to the aGVHD organ staging at initiation of AAT/PTM (i.e., aGVHD organ staging collected at pre-therapy visit if available, and the maximum GVHD organ staging within 72 hours prior to enrollment if not available). The analysis population will include the mITT patients, i.e., those who initiate their assigned study therapy. A logistic mixed model will evaluate the effect of treatment arm on Day 28 overall response with adjustment for treatment center and MN risk as specified in Section 7.4.1.1.

Moreover, the effects of duration from the initiation of corticosteroid to the initiation of IMP (<= 24 hours vs. 24-48 hours vs. 48-72 hours vs. 72 hours or more) and dose of corticosteroid on Day 28 post-randomization (>= 2mg/kg/day vs. 1.00-1.99 mg/kg/day vs. 0.26-1.00 mg/kg/day vs. 0.25 mg/kg/day or less, prednisone-equivalent) on Day 28 overall response will be evaluated using logistic mixed models that adjust for treatment center-group and MN risk. These analyses will use the mITT population.

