2.5.2 Corticosteroids (CS)

2.5.2.1 CS Dosing and Taper

All patients enrolled on this trial must receive CS at a minimum dose of prednisone 2 mg/kg/day PO (or methylprednisolone 1.6 mg/kg/day IV) divided into 1-2 daily doses as therapy for acute GVHD for at least 72 hours post enrollment. For patients that weigh over 100 kg, maximal starting dose of prednisone will be 200 mg (or methylprednisolone-equivalent). For calculation of subsequent CS doses/kg on subsequent measures, the modified starting weight of 100 kg will be used. For patients less than 100 kg, dosing of steroids may follow institutional practices (with respect to actual versus adjusted weight). Daily dose per kg is based on the weight of the patient at time of enrollment.

For responding patients with evidence of improvement in signs and symptoms of acute GVHD after treatment initiation, a suggested CS taper is provided below or may follow institutional practice. ***However, taper must not start sooner than 72 hours after enrollment and the CS dose must not be tapered to less than 0.25 mg/kg/day prednisone-equivalent (or 0.2 mg/kg/day methylprednisolone) before Day 29.*** A suggested taper schedule is provided below.

Table 2-2 Suggested Steroid Taper for Responding Patients

Suggested taper for responders (Prednisone/Methylprednisolone)	
Days 1-5	2 mg/kg/day (please note that taper cannot start until 3 days after enrollment)
Days 6-10	1.5 mg/kg/day
Day 11-15	1.0 mg/kg/day
Days 16-20	0.5 mg/kg/day
Days 21-28*	0.25 mg/kg/day
Days 29-56	Gradual further taper with a goal of reaching < 0.2 mg/kg/day of prednisone (or < 0.16 mg/kg/day of methylprednisolone) by Day 56.

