Overall response at Day 28 is defined as having a complete or partial response at Day 28, i.e. having partial or complete resolution of acute GVHD symptoms in some organ(s) without worsening in any other(s) along with being alive, free of any next-line GVHD therapy, and free of escalation of prednisone-equivalent steroid dose to 2.5mg/kg/day or more. Patients who have an escalation of prednisone-equivalent steroid dose to 2.5mg/kg/day or higher will be classified as NR with the following exception: if a patient received a prednisone-equivalent dose of 2.5mg/kg/day or more on the randomization day, maintaining this starting dose is not automatically considered an NR, but escalation to a dose higher than the starting one is an NR; moreover, if their dose is tapered below 2.5 mg/kg/day and later re-escalated to 2.5 mg/kg/day or above, they will be classified as an NR.

Organ staging is performed by MAGIC criteria, shown in Table 6. Patients with a missing Day 28 acute GVHD assessment will be classified as non-responders (NR). A Day 28 acute GVHD assessment conducted out of window (refer to Section 7.1 for visit window definition) will be considered as missing.

A supplementary analysis described in Section 7.4.3.4 will include adjustment for the refined Minnesota risk category and the MAGIC biomarker risk score (Srinagesh et al. 2019). The MAGIC biomarker risk score will be computed from baseline levels of ST2 and REG3 α per the following algorithm:

- For each patient, compute their estimated 6 month non-relapse mortality risk \hat{p} according to

$$\log(-\log(1 - \hat{p})) = -11.263 + 1.844 \log_{10} ST2 + 0.577 \log_{10} REG3\alpha$$

- If $\hat{p} < 14.1\%$, biomarker score = 1; else if $\hat{p} > 29.0\%$, biomarker score = 3; else, biomarker score = 2

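### SAP 7.4.3.4 models Day 28 steroid dose as an influence on same-day response; the coefficient cannot be read as an effect of dose, and the bands overlap

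*SAP*

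**What the plan says.** SAP 7.4.3.4 (Supplementary Analyses) names two explanatory variables for Day 28 overall response: the time from starting corticosteroid to starting study drug, and the "dose of corticosteroid on Day 28 post-randomization". Their effects "on Day 28 overall response will be evaluated using logistic mixed models that adjust for treatment center-group and MN risk". Treatment arm is not named as a covariate for these models. "These analyses will use the mITT population".

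The dose has four bands: 2 mg/kg/day or more, then "1.00-1.99 mg/kg/day vs. 0.26-1.00 mg/kg/day", then 0.25 or less. The timing bands are 24 hours or less, then "24-48 hours vs. 48-72 hours vs. 72 hours or more".

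Three other provisions bear on how the Day 28 dose arises:

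- **Taper.** Protocol 2.5.2.1 introduces its suggested taper with "For responding patients with evidence of improvement in signs and symptoms of acute GVHD after treatment initiation", and allows institutional practice instead. Table 2-2 puts 1.0 mg/kg/day at Days 11-15 and 0.25 mg/kg/day at Days 21-28, with no taper below 0.25 before Day 29.
- **Flare.** Protocol 2.5.3.4 lets the treating physician raise the dose on flare, to below 2.5 mg/kg/day.
- **Endpoint.** SAP 6.2 requires a responder to be "free of escalation of prednisone-equivalent steroid dose to 2.5mg/kg/day or more". A patient already at 2.5 mg/kg/day or more on the randomization day who merely maintains that dose is not automatically a non-responder.

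**The concern.** An explanatory variable should precede the outcome it is meant to explain. Here both are read on the same day, four weeks after randomization, and the protocol gives reasons for the dose to follow the course of the disease: down with improvement, up with flare. Part of the association is also fixed by definition through the escalation rule. A model of this kind can show that lower dose goes with better response even if dose does nothing. The SAP calls the result an effect on the primary endpoint variable and gives no caution on reading it. What is at stake is one misleading estimate in the study report, not the trial's conclusion.

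**Working it through.** The SAP gives no figure for this model, so there is nothing of its own to reproduce. The check has three parts.

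**1. Direction of the link.** Table 2-2 ends at 0.25 mg/kg/day on Days 21-28, and tapering below that is not allowed before Day 29. The lowest band (0.25 or less) is therefore where a patient who improves and follows the suggested taper stands on Day 28. A patient who flares may be moved up. A patient escalated to 2.5 or more and still there on Day 28 falls in the top band and is a non-responder by definition. All three push low dose towards response and high dose towards non-response, whatever dose itself does.

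**2. How large an association can arise with no effect of dose.** The documents give no distribution of Day 28 dose by response, so the shares below are assumptions. Band order is 0.25 or less / 0.26-1.00 / 1.00-1.99 / 2 or more. If response alone sets the band, the odds ratio of response for lowest versus highest band is (responder share lowest ÷ responder share highest) ÷ (non-responder share lowest ÷ non-responder share highest).

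| Assumed link | Responders (%) | Non-responders (%) | Odds ratio | Simulated trials with p < 0.05 |
|---|---|---|---|---|
| None | 30/40/20/10 | 30/40/20/10 | (0.30/0.10)/(0.30/0.10) = 1.0 | 5.0% |
| Mild | 30/50/15/5 | 20/45/25/10 | (0.30/0.05)/(0.20/0.10) = 3.0 | 38% |
| Moderate | 40/45/12/3 | 15/35/30/20 | (0.40/0.03)/(0.15/0.20) = 17.8 | 99% |
| Strong | 50/42/7/1 | 5/30/35/30 | (0.50/0.01)/(0.05/0.30) = 300 | 100% |

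The last column comes from 2,000 simulated trials per row, each with 136 patients and response rates of 50% and 75%, using a 3-df chi-square test of band against response at 5%. It is a simplified stand-in for the SAP's mixed model, without center-group or MN risk.

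Collapsing to low versus higher dose gives the same picture. If 60% of responders and 40% of non-responders are on a low dose, the odds ratio is (0.6/0.4)/(0.4/0.6) = 2.25; at 80% and 20% it is (0.8/0.2)/(0.2/0.8) = 16.

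As a side check, treatment arm was added to the model in a large simulated sample. Its odds ratio stayed at about 3.0 in every row, which is (0.75/0.25)/(0.50/0.50). If dose depends only on response, the problem lies in the dose coefficient rather than the treatment comparison.

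**3. The bands.** Assigning boundary values as written:

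- 1.00 mg/kg/day falls in both 1.00-1.99 and 0.26-1.00.
- Values between 0.25 and 0.26, and between 1.99 and 2.00, fall in no band unless doses are rounded to two decimals.
- 24, 48 and 72 hours each fall in two timing bands.

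A related gap: SAP 6.1 counts deaths as non-response, but a patient who dies before Day 28 has no Day 28 dose. SAP 7.4.3.4 does not say how such patients enter the model.

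**The case against.** The best defence is that nothing depends on this model. SAP 7.1 treats any testing outside the hierarchy as descriptive, and SAP 7.4.3.5 judges efficacy on the primary analysis alone. The table shells, which would fix the presentation, are a separate document not available here. All of that stands, and it limits the weight of the point. It does not make the estimate interpretable.

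A reader might infer three stronger things that the documents do not support.

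- **That the result simply is reverse causation and will be strong.** The taper schedule is only suggested and may follow institutional practice. Protocol 2.5.3.3 allows next-line therapy after 72 hours for progression or from Day 7 for non-response. Such patients are non-responders for the primary endpoint whatever their steroid dose, and some may be on low doses by Day 28. Steroids also treat GVHD. The strength of the link is unknown, and under the mild assumption only 38% of simulated trials were significant.
- **That the top band holds only patients who cannot respond.** The rule concerns escalation to 2.5 or more, while the band starts at 2. Patients between 2 and 2.5 are not non-responders by this rule, and maintained starting doses of 2.5 or more are excepted. The rule also looks at any escalation before the assessment, not at the Day 28 dose itself. The overlap is partial and of unknown size.
- **That the shared boundary will misplace many patients.** In Table 2-2 the 1.0 mg/kg/day step is at Days 11-15, so 1.00 on Day 28 is an edge case, though a realistic value for a slower taper.

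**Conclusion.** The point holds as a minor one. The coefficient for Day 28 dose mixes reverse causation, confounding by severity and any true effect, and the planned model cannot separate them. It may show lower dose with better response when dose has no effect, so it cannot be read as an effect of dose. That conclusion rests on the timing of the measurement and on the protocol's own taper, flare and endpoint rules. The sizes shown (odds ratios from 2.25 to 300) rest wholly on assumed band shares and illustrate what is possible rather than predict what will be seen. The overlap at 1.00 mg/kg/day and at 24, 48 and 72 hours is plain from the text. The primary efficacy decision is unaffected.

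**What to change.** In SAP 7.4.3.4, remove Day 28 dose as an explanatory variable from the logistic mixed model. Keep it as an outcome compared between arms, as SAP 7.6.6 already plans. If a link with response is of interest, tabulate Day 28 dose by response status and arm, with a row for patients who have no Day 28 dose, and do not call it an effect.

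Make any dose bands mutually exclusive and exhaustive, for example 0.25 or less; above 0.25 to below 1.00; 1.00 to below 2.00; 2.00 mg/kg/day or more. Do the same for the timing bands at 24, 48 and 72 hours.

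Baseline dose should not be put in as a replacement without first checking that it varies enough. Protocol 2.5.2.1 requires at least 2 mg/kg/day prednisone, or the methylprednisolone equivalent, for at least 72 hours after enrollment, so values are likely to cluster. It would also answer a different question.

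The cost is a short edit to one SAP section and the loss of one descriptive model. SAP section 1 allows revisions before the database hard lock. After lock, a caveat and a documented boundary rule in the report would serve.

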7.4.3.5 DECISION CRITERION

The findings from the primary analysis alone will be used to judge efficacy of AAT in comparison to PTM for the primary endpoint at the final analysis. If the primary analysis test statistic falls above the efficacy boundary, the study team will conclude that significant evidence of efficacy has been demonstrated; otherwise, the conclusion is that insufficient evidence of efficacy exists.

7.5 ANALYSIS OF SECONDARY ENDPOINTS

7.5.1 DURATION OF RESPONSE (DOR)

DOR will be evaluated in the set of patients in the ITT population who achieve a response (CR/PR) at Day 28. DOR will be estimated using the Kaplan-Meier estimator, with the probability of having a durable response, i.e. retaining the CR/PR, evaluated at 6 and 12 months post-randomization. Estimates and 95% CIs for the median and quartiles of the DOR will be obtained from the Kaplan-Meier estimator using the inverse Kaplan-Meier method described in Andersen et al. 1993. DOR will be compared from Day 28 to 12 months post-randomization between arms using a log rank test. DOR will also be displayed graphically using Kaplan-Meier curves with numbers of subjects at risk at specific time points presented for each treatment group.

Primary and supplementary analyses will be performed. In the primary analysis, DOR is defined as stated in section 6.3.1, as the time from Day 28 response to progression of acute GVHD, any next-line GVHD therapy, escalation of prednisone-equivalent steroid dose to 2.5mg/kg/day or more, or death from any cause. Its estimand is displayed in **Table 18**. The clinical question of interest is: what is the difference in duration of response between AAT combined with corticosteroids versus PTM combined with corticosteroids in patients with high risk acute GVHD following allogeneic HSCT who attain a Day 28 overall response, regardless of discontinuation of study treatment?

Table 18: Estimand for Duration of Response - Primary Analysis

Estimand Attribute	Definition		
Variable	Duration of Response; refer to Sections 6.3.1 and 7.9, and above for details		
Treatment	AAT (+corticosteroids) or PTM (+corticosteroids), refer to Section 2.1 for details		
Population	Patients with high risk acute GVHD following allogeneic HSCT who attain a Day 28 overall response		
Intercurrent Events	Event	Strategy	Description

Estimand Attribute	Definition		
	1. Acute GVHD progression	Composite strategy	Classified as an event
	2. Death	Composite strategy	Classified as an event
	3. Initiation of additional systemic aGVHD treatment ¹	Composite strategy	Classified as an event
	4. Discontinuation of study treatment	Treatment policy	No effect on variable
Population-level Summary	Median and quartiles with 95% CIs for each arm; probabilities of durable response at 6 and 12 months by arm; log rank test p-value comparing arms from Day 28 to 12 months post-randomization		

¹ Includes next-line GVHD therapy and escalation of prednisone-equivalent steroid dose to 2.5mg/kg/day or more.

For the supplementary analysis, DOR is defined as the time from Day 28 response to any next-line GVHD therapy, escalation of prednisone-equivalent steroid dose to 2.5mg/kg/day or more, or death from any cause; the corresponding estimand is shown in **Table 19**. The clinical question of interest is similar to the one for the primary analysis of DOR with the only difference being the definition of DOR.

Table 19: Estimand for Duration of Response - Supplementary Analysis

Estimand Attribute	Definition		
Variable	Duration of Response, refer to Sections 6.3.1 and 7.9, and above for details		
Treatment	AAT (+corticosteroids) or PTM (+corticosteroids), refer to Section 2.1 for details		
Population	Patients in Intention-to-treat Population who attain a Day 28 overall response		
Intercurrent Events	Event	Strategy	Description
	1. Acute GVHD progression	Treatment policy	No effect on variable
	2. Death	Composite strategy	Classified as an event
	3. Initiation of additional systemic aGVHD treatment ¹	Composite strategy	Classified as an event
	4. Discontinuation of study treatment	Treatment policy	No effect on variable
Population-level Summary	Median and quartiles with 95% CIs for each arm; probabilities of durable response at 6 and 12 months by arm; log rank test p-value comparing arms from Day 28 to 12 months post-randomization		

¹ Includes next-line GVHD therapy and escalation of prednisone-equivalent steroid dose to 2.5mg/kg/day or more.

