1.4 Study Hypothesis and Design

Identification and novel treatment strategies for patients at risk for steroid resistance remains a major unmet clinical need. In this context it is hypothesized that administration of additional immune suppression capable of increasing response rates without toxicity will limit further progression of GVHD and improve outcomes. Reflective of the above advancements in risk stratification for patients with newly diagnosed acute GVHD, we propose enrolling patients with newly-diagnosed Minnesota HR, isolated lower GI Stage 2 or Lower GI stage 1 plus any skin onto a prospective, double-blind, randomized, phase III trial of prednisone at a dose of 2 mg/kg/day (or methylprednisolone- equivalent) plus α_1 - Antitrypsin (AAT) or placebo.

Our hypothesis is that the addition of the AAT, Zemaira[®], a therapy with a demonstrated safety record as well as pre-clinical and clinical data in the setting of acute GVHD, will improve Day 28 acute GVHD response when added to CS in patients with newly diagnosed, HR acute GVHD. Patients who achieve a CR or PR to GVHD treatment at Day 28 have improved long-term outcomes (survival and NRM) when compared to non-responders and serves as a validated primary endpoint for acute GVHD trials.

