5.3.2.1 Stratified Mixed Effects Logistic Simulation

We simulated a stratified randomized block design using blocks of size 6, based on the distribution of patients observed in each center of the BMT CTN 1501 study. Centers with fewer than 10 patients were combined resulting in a total of 6 centers of size 23, 19, 17, 15, 14 and 48. We assumed these centers are a random sample from a larger population with standard deviations 0.05, 0.6 and 1.0. Additionally, we estimated that 35% of the patients will be classified as “high risk”; a covariate that we adjust for in all the simulations done

Simulation results indicate that in the absence of a random effect (i.e., when the standard deviation of the random effect is close to zero) our statistical power is at least 94.2% to detect an odds ratio of 3. Further, when the random effect is present (std. dev. of 0.6 and 1.0) statistical power is at least 92.9% and 90.1% to detect an odds ratio of 3 as shown in Table 5-3. We also obtain statistical power ranging from 20.8% to 25.5% when the odds ratio is 1.5 regardless of the variability between centers.

Table 5-3 Stratified Mixed Effects Logistic Model with 1000 Simulations of Size 136

Effect Size	Power (%)				
	Variance of Random Effects				
AAT - PTM	Odds Ratio	Coef.	0.0025	0.36	1.0
10%	1.500	0.406	25.5	24.2	20.8
15%	1.857	0.619	53.8	51.3	48.4
20%	2.500	0.916	85.0	83.4	79.6
25%	3.000	1.099	94.2	92.9	90.1

5.3.3 6 Month Analysis for Clinical Study Report

A clinical study report for potential regulatory submission will be prepared after all randomized subjects have completed at least 6 months of follow-up post-randomization. The database will be locked to support this clinical study report. Data transfer and unblinding will follow the study's Blinding Management Plan. This report will include descriptive statistics based on available data at time of the analysis as well as formal hypothesis testing / treatment comparisons for the primary Day 28 overall response rate (CR/PR) endpoint and secondary endpoints including GVHD-free

survival, proportion of response, proportion of response allowing for next-line therapy, and systemic infections.

The BMT CTN 1705 Statistical Analysis Plan (SAP) will elaborate further on the contents of the 6-month report.

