2. Duration of Response, Primary Definition: The log-rank test for comparing the DOR from Day 28 to 12 months post-randomization from the primary analysis as specified in **Section 7.5.1** (two-sided at 5% level)
3. Duration of Response, Supplementary Definition: The log-rank test for comparing the DOR from Day 28 to 12 months post-randomization from the supplementary analysis as specified in **Section 7.5.1** (two-sided at 5% level)
4. Non-relapse Mortality: The Gray's test for comparing the cumulative incidence of NRM from randomization to 12 months post-randomization as specified in **Section 7.5.2** (two-sided at 5% level)
5. Overall Survival: The log-rank test for comparing the OS from randomization to 12 months post-randomization from the primary analysis as specified in **Section 7.5.3** (two-sided at 5% level)

6. Progression-free Survival: The log-rank test for comparing the PFS from randomization to 12 months post-randomization from the primary analysis as specified in **Section 7.5.4** (two-sided at 5% level)
7. GVHD-free Survival at Day 56: The Wald test from the logistic mixed model as specified in **Section 7.5.5** (two-sided at 5% level)

The gatekeeping procedure evaluates the endpoints sequentially in the order displayed and ends if the one-sided test or two-sided test for an endpoint fails to find a significant result showing superiority of AAT to PTM, precluding further testing of any remaining endpoints in the hierarchy. This strategy ensures control of the one-sided familywise type I error rate at 2.5% and permits claims of confirmatory benefit for any endpoint(s) where superiority of AAT is demonstrated. Any hypothesis testing performed outside the hierarchy is deemed descriptive in this study.

Analyses for several endpoints involve adjustment for center effects through regression modeling. Because the average number of patients enrolled per center is expected to be small ($136/25 \approx 5.5$), centers will be combined into center-groups for these analyses to ensure the stability of the models. This will be done by including the top 5 enrolling centers each as a separate group and combining all other centers into a sixth catchall group.

All efficacy analyses will be conducted using the ITT population unless otherwise specified.

Table 14: Endpoints for Analysis Under Each Analysis Population

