7.9 MISSING DATA AND SENSITIVITY ANALYSIS

Regarding endpoints involving acute GVHD response to study treatment (overall response, DOR, GVHD-free survival, acute GVHD response, organ-specific response), any patient with a missing acute GVHD assessment at the evaluation day will be classified as a non-responder (NR) at that time point.

For the duration of response (DOR), a patient with a missing acute GVHD assessment will be considered as a failure at that time point.

For GVHD-free survival, a patient with either a missing acute or chronic GVHD assessment will be considered as a failure at that time point.

For time-to-event outcomes other than DOR and GVHD-free survival (NRM, OS, PFS, chronic GVHD, relapse/progression), patients that withdraw or are lost to follow-up are assumed to be censored at random.

For other endpoints, the occurrence of missing data, whether due to the patient’s missing assessment(s) or withdrawal from the study, is assumed to occur randomly.

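### Two duration-of-response tests, run only in Day 28 responders and so not randomised comparisons, carry confirmatory claims and gate NRM, OS, PFS and GVHD-free survival

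*SAP*

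**What the plan says.** SAP 7.1 sets a gatekeeping sequence of seven tests. Step 1 is Day 28 overall response. Step 2 is "Duration of Response, Primary Definition: The log-rank test for comparing the DOR from Day 28 to 12 months post-randomization", and step 3 repeats it with the supplementary DOR definition, which no longer counts acute GVHD progression as an event. Steps 4 to 7 are NRM, OS, PFS and Day 56 GVHD-free survival.

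A step without significant superiority of AAT ends the procedure, "precluding further testing of any remaining endpoints in the hierarchy". The same section says that the strategy "permits claims of confirmatory benefit for any endpoint(s) where superiority of AAT is demonstrated".

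SAP 7.5.1 fixes who enters steps 2 and 3: "DOR will be evaluated in the set of patients in the ITT population who achieve a response (CR/PR) at Day 28". Table 18 limits the population in the same way, and Table 19 gives it as "Patients in Intention-to-treat Population who attain a Day 28 overall response". Steps 1 and 4 to 7 use all randomised patients (SAP 5.1, 7.4.3.1 and 7.5.2 to 7.5.5).

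Protocol 5.7.1 also compares DOR between arms among responders, but the protocol contains no testing sequence. SAP 7.11 names the significance level for exploratory endpoints as its only change from the protocol.

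**The concern.** Randomisation balances the arms in all randomised patients. It does not balance those who respond on AAT against those who respond on placebo. Step 2 is opened only by a significant effect of AAT on response, so whenever it is tested for a confirmatory claim there is already evidence that treatment changed who is in the set. A difference in DOR may then reflect longer responses, a different mix of responders, or both.

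Two things are at stake. A significant DOR result could be reported as confirmed longer response when part of it is selection. A non-significant one removes confirmatory status from four endpoints analysed in all randomised patients, on the strength of a comparison that randomisation does not protect.

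**Working it through.** **Inputs from the documents.** 68 patients per arm, Day 28 response 50% against 75%, one-sided 2.5%, 86% power (protocol 5.2, SAP 4.2); follow-up of 12 months. Neither document gives a DOR event count, hazard ratio or power.

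**The plan's own figure.** Pooled two-sample Z-test with mean rate 0.625:
- Critical difference: 1.96 × √(2 × 0.625 × 0.375 / 68) = 1.96 × 0.0830 = 0.163, as in SAP Table 4.
- Standard error under the alternative: √((0.25 + 0.1875) / 68) = 0.0802.
- Power: Φ((0.25 − 0.163) / 0.0802) = Φ(1.09) = 86.2%. The stated 86% is reproduced; the futility look lowers it by only about 0.1 point.

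**Who is compared at step 2.** Placebo responders: 68 × 0.50 = 34. AAT responders: 68 × 0.75 = 51. If response is monotone (anyone who responds on placebo would also respond on AAT), 51 − 34 = 17 of the 51, one third, have no placebo counterpart.

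**Size of the selection effect (assumptions).** Patients who would respond on either arm keep their response to 12 months with probability 60%. Protocol 1.1 gives about 50% responding and 30% responding durably, 30/50 = 60%, but states no time horizon, so 60% is illustrative. AAT has no effect on anyone's durability. The added responders have durability d, so AAT responders average (2/3) × 60% + (1/3) × d. Event times are exponential and the test is a log-rank test in responders with |z| > 1.96. Each cell shows a run of 8,000 trials, then one of 20,000.

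| d | AAT responders' average | Favours AAT | Favours placebo |
|---|---|---|---|
| 60% | 60.0% | 2.7% / 2.7% | 2.5% / 2.2% |
| 75% | 65.0% | 7.4% / 7.3% | 0.7% / 0.6% |
| 85% | 68.3% | 13.3% / 12.8% | 0.2% / 0.3% |
| 90% | 70.0% | 15.8% / 16.6% | 0.2% / 0.2% |
| 40% | 53.3% | 0.6% / 0.5% | 8.8% / 8.5% |
| 30% | 50.0% | 0.3% / 0.2% | 14.5% / 14.0% |
| 20% | 46.7% | 0.1% / 0.1% | 22.9% / 23.6% |

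The Monte Carlo standard error is at most about 0.5 point. Restricting to trials in which step 1 passed leaves the rates almost unchanged: 7.4% and 16.7% for AAT at d = 75% and 90%, 8.6% and 23.5% for placebo at d = 40% and 20%.

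**What the gate does if AAT adds responders with unchanged durability.** Response, DOR and NRM were simulated jointly, with responders' non-relapse deaths counted as DOR events. Steps 1 and 2 both pass in under 3% of trials, so NRM is formally tested in at most that share. If NRM stood second, the chance of confirming it would depend on assumed 12-month NRM in responders and non-responders:

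| NRM, responders / non-responders | By arm, placebo vs AAT | NRM confirmed if second |
|---|---|---|
| 25% / 55% | 40% vs 32.5% | about 14% |
| 20% / 60% | 40% vs 30% | about 23% |
| 15% / 65% | 40% vs 27.5% | about 33% to 34% |

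By-arm values are weighted averages, for example 0.75 × 20% + 0.25 × 60% = 30%. In the present order NRM is confirmed in under 2% of trials in all three cases. That is an upper bound, because step 3 was not simulated.

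**The case against.** The case for the plan has real weight.

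- **Error control.** A reader might infer that the sequence inflates the familywise error. It does not: for the hypotheses as written, equal DOR among each arm's responders, a fixed sequence at these levels is valid. The weakness lies in what that hypothesis means.
- **Disclosure and order.** Tables 18 and 19 state the conditional population openly, and DOR is listed first among the secondary objectives (protocol 2.3.2, SAP 3.3). This stands, but disclosure does not make the contrast randomised.
- **Rationale.** A reader might infer that DOR does not belong in this trial, or that testing it early contradicts the design. The documents do not support that. Day 28 responders continue study drug on Days 35 to 56 (protocol 1.6 and 2.5.1.7), protocol 1.6.3 reports a view that longer maintenance may be needed, and 1.1 and 1.3.2 describe poor durability as part of the unmet need.
- **Direction.** A reader might infer that the design favours a false AAT claim. That requires the added responders to be more durable than the others. Protocol 1.3.2 reports that patients with the highest biomarker risk respond less often and less durably; if the extra responders came from that group, the bias would run against AAT. The documents do not settle this.
- **The under-3% figure.** It should not be read as the size of the defect. With unchanged durability the step 2 null is true, and any fixed sequence would stop there about as often.
- **Power.** NRM is also weakly powered. Under assumed rates and equal prognosis of added responders, the DOR test passes in 13% to 23% of trials at a hazard ratio of 0.7 and 34% to 59% at 0.5, against 21% to 28% and 54% to 71% for NRM. At equal hazard ratios reordering gains only moderate power. NRM, OS, PFS and GVHD-free survival are estimated and reported in either order.

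**Conclusion.** The point holds in a limited form and is worth acting on because the change is cheap. DOR among responders is a sound description and a legitimate endpoint. What the design cannot support is an unqualified confirmatory claim from it, or its role as gate to four endpoints that are compared as randomised.

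With no true effect on durability, the chance of a significant step 2 result in favour of AAT is about 7% to 17% instead of 2.5% if the added responders are 75% to 90% durable. It is below 1% if they are 20% to 40% durable, when placebo is significantly favoured in about 8% to 24%. With equal durability the test keeps its nominal size. These figures rest on 60% durability in common responders, monotone response and exponential times, none of which the documents fix. They show that selection can matter, not that it will.

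Moving DOR gives access to the NRM test. It does not assure success there: about 14% to 34% under the assumed NRM rates, with OS, PFS and GVHD-free survival still behind it.

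**What to change.** In SAP 7.1, either make both responder-only DOR tests descriptive or move them to the end: response, NRM, OS, PFS, GVHD-free survival, then the two DOR tests. In either case add a sentence such as: *DOR is compared among Day 28 responders, a set defined after randomisation; the result is conditional on response and is not a randomised comparison.* Leave the DOR definitions and cohort as they are.

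Record the change and its reason in SAP 7.11. SAP section 1 allows revisions until the database hard lock, but the practical deadline is earlier. For the 6-month report, protocol 5.3.3 says: "The database will be locked to support this clinical study report. Data transfer and unblinding will follow" the study's blinding plan. A reorder after that point would look driven by the data. The documents do not date this lock; if it has passed, keep the order and add only the qualifying sentence.

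The cost is text in two SAP sections, with no change to data collection, sample size or the primary analysis. The trial gives up, or places last, a confirmatory DOR claim, and the testing order departs from the order of the listed objectives.
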